- Cohorts 1 and 2 (Q2W): Alirocumab injections will be prepared from vials by the pharmacist (or equivalent). Detailed instructions on preparation of injections from vials will be provided in a separate document. Alirocumab injections will be administered at Weeks 0, 2, 4, and 6. The Weeks 0 and 4 alirocumab injections will be administered at the clinical site by the site staff. The Weeks 2 and 6 alirocumab injections will be administered at the clinical site by the site staff or at the patient's home by a health care professional, depending upon local arrangements and preferences of the investigator/patient.
- Cohort 3 (Q4W): Alirocumab injections will be prepared from vials by the pharmacist (or equivalent). Detailed instructions on preparation of injections from vials will be provided in a separate document. Alirocumab injections will be administered at Weeks 0 and 4 at the clinical site by the site staff.
- Cohort 4 (Q4W): Alirocumab injections will be administered with prefilled syringes. Alirocumab injections will be administered Week 0, Week 4, and Week 8 at the clinical site by site staff.
- The lipid results from specimens obtained during the open-label dose finding treatment period will be masked for the clinical site/Investigator and patients. No attempts should be made by the investigator or patient to routinely have the patient's lipid values independently evaluated after entry into the open-label dose finding treatment period and until the final follow-up visit for Cohort 1, Cohort 2, and Cohort 3, and entry into the OLE period for Cohort 4. The sponsor and the DMC will closely monitor the lipid results during the 8-week open-label dose finding treatment period. If any safety concerns are noted during this period, including very low LDL-C levels (ie, LDL-C <50 mg/dL [1.30 mmol/L] on one or more occasion), then appropriate action will be taken by the Sponsor in consultation with the DMC.

Follow-Up Period, only for Cohorts 1 to 3:

- A follow-up period (off treatment) of 6 (Cohort 3) or 8 weeks (Cohorts 1 and 2) after the end of open-label dose finding treatment period visit. For these 3 cohorts, the final follow-up visit corresponds to 10 weeks after the last alirocumab injection administered during the open-label dose finding treatment period, since the last injection for Cohorts 1 & 2 is Week 6 and for Cohort 3 it is Week 4.

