During the open-label extension period for Cohort 3, the first injection administration will start at Week14 after the last injection administration at Week 4 (ie, 10 weeks after the last administration of alirocumab). The treatment kit number will be provided by IRT according to the last dose administered in Cohort 3. The first injection of the extension period will be done at the site by the investigator staff. If the self-injections by patient or another designated person (such as parent, nurse, etc.) are decided during the extension period a training injection should be planned 4 weeks before the first self-injection, under direct site staff supervision.

During the open-label extension period for Cohort 4, the first injection administration will start at Week 12 at the end of the 12-week open-label dose finding. The treatment kit number will be provided by IRT according to the last dose administered in Cohort 4. The first injection of the extension period will be done at the site by the investigator staff. If the self-injections by patient or another designated person (such as parent, nurse, etc.) are decided during the extension period a

training injection should be planned 4 weeks before the first self-injection, under direct site staff supervision.

During the extension treatment period, IMP should ideally be administered every 2 weeks SC or every 4 weeks at approximately the same time of the day; however it is acceptable to have a window period of ± 3 days. The time of the day is based on visit's time or patient's preference in case of self-injections.

If by mistake or due to other circumstances an injection is delayed by more than 7 days or completely missed (for Cohorts 1 and 2) or by more than 14 days or completely missed (for Cohort 3 and Cohort 4), then the patient should return to the original schedule of study treatment administration without administering delayed injections. On the other hand, if the delay is less than or equal to 7 days (for Cohorts 1 and 2) from the missed date or if the delay is less than or equal to 14 days for (Cohort 3 and Cohort 4) from the missed date, then the patient should administer the delayed injection and then resume the original schedule of study treatment administration.

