9.2.3 Safety endpoints

The safety endpoints will be adverse events, serious adverse events, adverse events of special interest, laboratory data, vital signs, Tanner stage assessment, body weight, and height assessed throughout the study.

9.2.3.1 *Observation period*

The observation of safety data will be as follows:

- Pretreatment period: The Pretreatment observation period is defined from the signed informed consent up to the first dose of IMP.
- Treatment emergent adverse event (TEAE) period: The TEAE observation period is defined as the time from the first dose of IMP to the last dose of IMP injection +70 days

(10 weeks) as residual effect of alirocumab is possible until 10 weeks after the stop of treatment IMP injection.

- Post-treatment period: The post-treatment observation period is defined as the time starting the day after the end of the TEAE period up to the end of the study (see definition in [Section 6.2.2](#)).

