- All evaluations performed for the end of the follow-up period are the same for the first visit of the open-label extension treatment period (see previous Section) except blood sample for lipids evaluation.
- Review patient's diet. Patient should be on a diet in accordance with the American Academy of Pediatrics guidelines (1) or equivalent.
- Check of stability of LMT dosing.
- Urine pregnancy test (females who have experienced menarche only).
- If the patient is confirmed eligible (and in fasting conditions), the Investigator will start the next study procedures:
 - IVRS/IWRS contact for open-label extension treatment allocation of one 7-digit treatment kit number according to the treatment number list for the alirocumab injections. Investigators should never allocate a treatment kit number to a patient without contacting IVRS/IWRS.
- If the prefilled syringe becomes available: open-label extension treatment IMP kits dispensation as per treatment kit numbers provided by IVRS along with schedule reminder. Injection training to be provided. The patient injection instruction manual and treatment administration package should be provided. The patient's diary should be given and instructions on its completion should be reviewed for Cohorts 1 to 3.
- The first open-label extension alirocumab injection will take place at the study site, but only after the collection of the fasting blood samples and after the assessment of all evaluations planned at this visit. Close supervision, feedback and training (if prefilled syringes) to be provided for IMP administration in case of self-injection or injection administered by parent/legal custodian.
- Obtain fasting blood sample for:
 - Lipids: total-C, calculated LDL-C, HDL-C, TG, non-HDL-C, Apo B, Apo A-1, ratio Apo B/Apo A-1, and Lp(a) for Cohorts 1 to 3,
 - Lipids: total-C, calculated LDL-C, HDL-C, TG, non-HDL-C for Cohort 4.
- Reminders:
 - An appointment will be given for the next study site visit,
 - Patient to bring the diary, and used and unused kits, at the next study site visit (if applicable ie, prefilled syringes).

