11 STATISTICAL CONSIDERATIONS

11.1 DETERMINATION OF SAMPLE SIZE

No power sample size calculations were performed for the main phase. A sample size of 10 patients per cohort is empirical and based on the sample size of the Phase 1 studies (R727-CL-904 and R727-CL-1001) conducted in adults. No less than 4 patients with BW <50 kg and no less than 4 patients with BW \geq 50 kg will be enrolled in 4 independent cohorts (Cohort 1, Cohort 2, Cohort 3, and Cohort 4), which will allow the evaluation of the pharmacokinetics/pharmacodynamics (PK/PD) profile and safety of different alirocumab doses/dose regimen in each BW category and to compare with PK/PD profile and safety observed in adult patients.

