2.4.4 Analyses of efficacy endpoints

For statistics where international and conventional units do not impact the results (eg, means and least square (LS) means for percent changes from baseline, rates of patients below a threshold), derivations will be done and statistical models will be run using conventional units. For other statistics (eg, descriptive statistics at baseline and over time, absolute changes from baseline), derivations will be done with both international and conventional units.

There will be no formal statistical test for the efficacy endpoints. All efficacy analyses will be descriptive.

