The binary endpoint at time point of interest will be derived from observed and imputed lipid values at this time point. Combined estimates for proportion of patients reaching the target for each alirocumab dose groups and for each cohort will be obtained through the SAS MIANALYZE procedure.

2.4.4.2.4 *Summary of results per time point*

For the open-label dose finding treatment period, central laboratory values (in conventional (US) and international units), percent change from baseline, and/or when appropriate absolute change from baseline (in conventional and international units), for calculated LDL-C, Total-C, HDL-C, fasting TG, and non HDL-C at each time point (including Week 10 and W12 time points for Cohort 4), for Lp(a), Apo-B, Apo-A1 and ratio Apo-B/Apo-A1 (absolute change from baseline) at Week 8 time points will be summarized in the mITT population using:

- For lipids other than TG and Lp(a): LS mean and SE for each alirocumab dose group, obtained from the same MMRM models as used for endpoints above and including planned time points (see [Section 2.4.4.2.1](#)) and with raw values, changes from baseline, or percent change from baseline as response variable in the model as appropriate.
- For TG and Lp(a): mean and SE for each alirocumab dose group obtained from multiple imputation approach followed by the robust regression models as used for endpoints above and including planned time points (see [Section 2.4.4.2.2](#)) and with raw values or percent changes from baseline as response variable in the model as appropriate.

In addition, quantitative descriptive summaries by time point (value at visit and % change from baseline) will be presented for all lipids using observed (ie, non-missing) data.

The time profile in %change from baseline of each parameter (except ratio ApoB/Apo A-1 where absolute change will be used) will be plotted according to alirocumab dose received by using LS mean and SE except for TGs and Lp(a). For these 2 parameters, the combined estimate for mean and SE will be used.

For OLDFI /OLE combined period, only quantitative descriptive summaries by time point during the OLDFI/OLE combined efficacy treatment period will be presented for all lipids using observed data in the mITT population. Lipid results pre- versus post-switch to the selected Phase 3 doses will be analyzed separately for Cohorts 1 to 3.

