The OLDFI/OLE combined efficacy treatment period is defined as the period from the first IMP injection to last OLE IMP injection + 21 days (for Cohorts 1 & 2) or +35 days (for Cohorts 3 & 4).

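### Visit 8 (Week 14/16) lipids of Cohort 1–3 extension entrants are off-drug values, yet the SAP's combined efficacy treatment period includes them unlabelled, against its own +21/+35-day limit

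*Protocol*

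**What the plan says.** **Timing of the sample.** Protocol 6.1 describes the follow-up of Cohorts 1–3 as off treatment and puts its final visit 10 weeks after the last main-phase injection, "since the last injection for Cohorts 1 & 2 is Week 6 and for Cohort 3 it is Week 4". Protocol 8.1.2 describes the first extension injection in the same way: "ie, 10 weeks after the last administration of alirocumab". Visit 8 closes the follow-up and opens the extension. Protocol 10.1.4.1 requires fasting lipids from extension entrants at that visit and states: "The first open-label extension alirocumab injection will take place at the study site, but only after the collection of the fasting blood samples". The end-of-follow-up assessments in Protocol 10.1.3.2 include no lipids, so patients who decline the extension have no such value.

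**Dose-finding rule.** SAP 2.3.1.1 and 2.4.4.1 end the dose-finding efficacy treatment period 21 days (Cohorts 1–2) or 35 days (Cohorts 3–4) after the last dose-finding injection. For extension entrants they also cut it on the day before the first extension injection.

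**Combined rule.** SAP 2.4.4.2.4 states: "The OLDFI/OLE combined efficacy treatment period is defined as the period from the first IMP injection to last OLE IMP injection + 21 days". That tail applies to the two Q2W cohorts; Cohorts 3–4 have 35 days. The section makes no exception for the follow-up gap. The lipid output planned there is limited: "only quantitative descriptive summaries by time point during the OLDFI/OLE combined efficacy treatment period will be presented for all lipids using observed data". The analysis set is mITT. SAP Table 4 gives Week 14/Week 16 its own time point.

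**The concern.** The SAP uses the term efficacy treatment period in two ways. Under the dose-finding rule, a lipid value 70 days after the last injection is outside the period. Under the combined rule, the same value in the same patient is inside it. No SAP passage marks the Week 14/16 row as off treatment.

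Long-term efficacy in the extension is a declared endpoint (Protocol 9.4.4), and this summary is its only planned lipid analysis. A table titled by the efficacy treatment period could show the LDL-C reduction shrinking at Week 14/16 and returning later, when the cause is a scheduled gap in dosing.

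The value also has a use that the plan does not state. The study has no control arm, and for Cohorts 1–3 this is the only scheduled off-drug LDL-C after baseline. Background lipid therapy was to stay unchanged until then, barring exceptional circumstances (Protocol 8.8.1).

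**Working it through.** No power or test calculation bears on this point. The Protocol says "No power sample size calculations were performed for the main phase" and the SAP says "There will be no formal statistical test for the efficacy endpoints". The check is study-day arithmetic, with study day = 7 × week + 1 (Day 1 is the first injection, as in SAP Table 3).

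**Inputs.** Injection and visit weeks come from Protocol 6.1 and 1.3.1. The dosing window is ±3 days (Protocol 8.1) and the Visit 8 window ±7 days (Protocol 10). The tails of 21 and 35 days come from SAP 2.3.1.1. The Week 14/16 analysis window runs from target −28 to target +27 (SAP Table 4).

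| Quantity | Cohorts 1–2 | Cohort 3 |
|---|---|---|
| Last dose-finding injection | 7×6+1 = Day 43 | 7×4+1 = Day 29 |
| Visit 8 | 7×16+1 = Day 113 | 7×14+1 = Day 99 |
| Gap | 113−43 = 70 days | 99−29 = 70 days |
| Gap with windows (±7 and ±3) | 60–80 days | 60–80 days |
| End of dose-finding efficacy period | 43+21 = Day 64 | 29+35 = Day 64 |
| Visit 8 beyond that end | 113−64 = 49 days | 99−64 = 35 days |
| Least excess with windows | 60−21 = 39 days | 60−35 = 25 days |
| Week 14/16 analysis window | Day 85–140 | Day 71–126 |

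1. **The plan's own figure.** 70/7 = 10 weeks, so the Protocol's stated interval is reproduced in all three cohorts.
2. **Classification.** At every permitted combination of windows, Visit 8 is outside the dose-finding efficacy period and inside the combined one.
3. **Capture.** Visit 8 can fall on Days 106–120 (Cohorts 1–2) or 92–106 (Cohort 3), always within its Table 4 window. The Week 8 window closes on Day 70. The next scheduled lipid visits are Week 28 and Week 26 (Days 197 and 183), with windows opening on Days 169 and 155. The pre-injection Visit 8 sample is thus the value shown at Week 14/16 and spills into no other row.
4. **Cohort 4.** The last main-phase injection is on Day 57 and the Week 12 sample on Day 85. The gap of 28 days is within the 35-day limit, so Cohort 4 is not affected.
5. **Possible size in the table.** Protocol section 4 gives Week 8 LS mean changes of −21.2% (Cohort 1), −46.1% (Cohort 2) and −7.7% (Cohort 3). Let *r* be the share of that change still present at Visit 8; the documents do not give it. The row would show *r* × the Week 8 change: 0 to −21.2%, 0 to −46.1% and 0 to −7.7% as *r* runs from 0 (complete washout) to 1. Protocol 9.2.3.1 says that "residual effect of alirocumab is possible until 10 weeks after the stop of treatment IMP injection", so *r* = 0 is an assumption.
6. **Reach.** At most the 31 patients of Cohorts 1–3 (Protocol section 4), less those who do not enter the extension.

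**The case against.** The strongest reply is that little can go wrong in practice, and much of it stands.

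- **Not pooled.** Week 14/16 has its own row, and SAP section 3 calls the combined lipid analysis exploratory. Primary and secondary Week 8 results exclude this value, and dose selection rests on the dose-finding period.
- **Not lost.** A reader might infer that the off-drug reading is discarded. The documents do not support that. SAP 2.4.4.2.4 describes by-visit summaries of value and percent change, SAP 2.1.3 fixes baseline before the first dose-finding injection, and SAP 2.4 presents results by cohort and dose group. Percent change from Week 0 to Week 14/16 is therefore already implied. What is absent is a label, a same-patient comparison and a stated purpose.
- **Not called on-treatment.** The SAP attaches that term to the dose-finding endpoints, not to the combined summary. The Protocol does identify the follow-up as off treatment.
- **Direction.** An off-drug row would understate long-term efficacy, not inflate it. In Cohort 3, with −7.7% overall and +4.0% in the heavier group, there was little effect to lose.
- **Weak as a drift check.** It covers extension entrants only, has no control and sits at the edge of the residual-effect period. Regression to the mean is already reduced, because eligibility uses the screening LDL-C while baseline is normally the separate Week 0 sample.

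These points limit the consequence. They do not remove the conflict between two definitions of the same kind of period.

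**Conclusion.** The point holds in a limited form. For Cohort 1–3 extension entrants, SAP 2.4.4.2.4 puts a lipid sample taken about 70 days after the last injection inside an efficacy treatment period, although the SAP's dose-finding limit passed 49 days earlier (Cohorts 1–2) or 35 days earlier (Cohort 3). This rests on planned timing and holds throughout the visit and dosing windows.

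The consequence is one unlabelled row in an exploratory descriptive table. The primary analysis, the secondary Week 8 endpoints and dose selection are not affected. How far the row would depart from Week 8 depends on the unknown residual effect; a value near zero needs complete washout.

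A reader might go further and take the Visit 8 value as a test of whether the Week 8 fall is drift. The design does not support that either: residual drug effect and drift could not be separated in this selected, uncontrolled group. A return towards baseline would be supportive evidence that the change reverses off drug, and no more.

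The change is still worth making: a stated rule misclassifies known off-drug values, and the remedy uses data already collected.

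**What to change.** In SAP 2.4.4.2.4:

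1. For Cohorts 1–3, define the combined efficacy treatment period in two segments: first to last dose-finding injection plus 21 or 35 days; then from after the first extension injection to the last extension injection plus 21 or 35 days. The Visit 8 sample and that injection share a date, so the second segment should start by date and time, or on the next day.
2. State where the period ends for patients who never enter the extension. The present wording refers only to the last extension injection, whereas SAP 2.1.4 gives a fallback to the last dose-finding injection for safety.
3. Keep the Visit 8 pre-injection lipids as a separate row labelled *off treatment, pre-extension*, and say that the row lies outside the efficacy period. Without this, the split alone would drop the value from the summary.
4. Show percent change from Week 0 in that row beside the Week 8 result for the same patients, by cohort, described as supportive.

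The cost is SAP wording and one descriptive table, with no new data and no change to the Week 8 analyses. The limits should be printed with the table: extension entrants only, no control, and sampling at the edge of the 10-week residual-effect period.

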8.5 PACKAGING AND LABELING

Open Label dose finding treatment period:

For Cohorts 1, 2 and 3: Each kit will contain one vial: either a vial of alirocumab 150 mg/mL or a vial solvent for alirocumab. The number of kits and types of kits (active or solvent) to be dispensed depend on the treatment doses / dose regimen (see [Table 1](#)).

For Cohort 4, patients will receive 1 or 2 kit(s) for the 12 week alirocumab treatment period depending on the dose group (1 kit for 150mg Q4W & 2 kits for 300mg Q4W). Each kit will contain 4 PFS of alirocumab 150 mg/mL

Open Label Extension period:

If PFS are available:

Cohorts 1 & 2: patients will receive 2 kits for 12-weeks alirocumab treatment period. Each kit will contain 4 PFS.

Cohort 3: patients will receive 1 kit for 12-weeks alirocumab treatment period. Each kit will contain 4 PFS.

Cohort 4: patients will receive 1 or 2 kit(s) of PFS for up to a 12 week alirocumab treatment period, depending on dose group.

If PFS are not available for Cohorts 1 to 3:

The packaging will be the same as for Open Label Dose finding:

Each kit will contain one vial: either a vial of alirocumab 150 mg/mL or a vial solvent for alirocumab. The number of kits and types of kits (active or solvent) to be dispensed depend on the treatment doses / dose regimen (see [Table 1](#)).

Packaging is in accordance with the administration schedule. The content of the labeling is in accordance with the local regulatory specifications and requirements.

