- The alirocumab injections should be done every 2 weeks for Cohorts 1 and 2 or every 4 weeks for Cohort 3 and Cohort 4 at clinical site, by a health care professional at patients' home, or by patient or representative (parent...) at home according to the type of supplied syringe (prefilled or not) during all the extension period. This alirocumab administration during the open-label extension will continue until approximately 10 weeks before the initiation of the pediatric Phase 3 study or December 2018, at the latest.

**10.1.4.2 Visit 9/Week 20 for Cohorts 1 & 2 /Week 18 for Cohort 3/Week 16 for Cohort 4
(Phone Call Option)**

- Collect AEs.
- Record concomitant medication.
- Review patient's diet. Patient should be on a diet in accordance with the American Academy of Pediatrics guidelines (1) or equivalent.
- Review patient's diary and compliance check of IMP if applicable.
- Check of stability of LMT dosing.
- Reminders:
 - An appointment will be given for the next study site visit,
 - Patient to bring the diary, and used and unused kits, at the next study site visit (if applicable ie, prefilled syringes).

**10.1.4.3 Visit 10/Week 24 for Cohorts 1 & 2 /Week 22 for Cohort 3/Week 20 for Cohort 4
(Phone Call Option)**

- Collect AEs.
- Record concomitant medication.
- Review patient's diet. Patient should be on a diet in accordance with the American Academy of Pediatrics guidelines (1) or equivalent.
- Check of stability of LMT dosing.
- Reminders:
 - An appointment will be given for the next study site visit,
 - Remind patient to be in fasting conditions (ie, overnight, at least 8 hours fast and refrain from smoking) for next study site visit. Also, alcohol consumption within 48 hours and intense physical exercise within 24 hours preceding the next study site visit are discouraged,
 - Patient to bring the diary, and used and unused kits, at the next study site visit (if applicable ie, prefilled syringes).

10.1.4.4 Visits 11, 13, 15, 17, 19 (every 24 weeks)/ Visit 11 only for Cohort 4

- Collect AEs.
- Record concomitant medication.
- Urine pregnancy test (females who have experienced menarche only).
- Review patient's diet. Patient should be on a diet in accordance with the American Academy of Pediatrics guidelines (1) or equivalent.

- If the prefilled syringe becomes available: Data collection on alirocumab administration and alirocumab compliance check by review of diary and treatment kit accountability for Cohorts 1 to 3.

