- Cohort 4 will receive second alirocumab allocation and administration for OLE phase.
- Check of stability of background LMT.
- IVRS/IWRS contact to get treatment kit number for 1 kit resupply.
- Obtain fasting blood sample for:
 - Lipids: total-C, calculated LDL-C, HDL-C, TG, non-HDL-C, Apo B, Apo A-1, ratio Apo B/Apo A-1, and Lp(a) for Cohorts 1 to 3.
 - Lipids: total-C, calculated LDL-C, HDL-C, TG, non-HDL-C for Cohort 4.
 - Liver panel (ALT, AST, ALP, and total bilirubin),
 - Hematology: red blood cell count including hematocrit, hemoglobin, WBC count with differential count and platelets,
 - Chemistry: glucose, sodium, potassium, chloride, bicarbonate, calcium, phosphorous, urea nitrogen, creatinine, uric acid, total protein, LDH, albumin, and γ GT,
 - CPK,
 - Anti-alirocumab antibodies,
 - Adrenal gland hormones: cortisol (with reflexive ACTH levels if cortisol <LLN), dehydroepiandrosterone sulfate (DHEAS),
 - Gonadal and pituitary hormones: testosterone (male) and estradiol (female), luteinizing hormone (LH), follicle-stimulating hormone (FSH),
 - Fat soluble vitamins: retinol (vitamin A), 25hydroxy-vitamin D (vitamin D), alpha-tocopherol (vitamin E), phylloquinone (vitamin K).
- Reminders:
 - An appointment will be given for the next study site visit,
 - Remind patient to be in fasting conditions (ie, overnight, at least 8 hours fast and refrain from smoking) for next study site visit. Also, alcohol consumption within 48 hours and intense physical exercise within 24 hours preceding the next study site visit are discouraged,
 - Patient to bring the diary, and used and unused kits at the next study site visit.

10.1.4.5 Visits 12, 14, 16, 18 (every 24 weeks)/ Visit 12 only for Cohort 4

- Collect AEs.
- Record concomitant medication.
- Perform physical examination.
- Get body weight and height measurements.
- Get Tanner stage measurement by the same investigator/designee at each visit if possible.

- Take vital signs including HR and BP.
- Urine pregnancy test (females who have experienced menarche only).
- Review patient's diet. Patient should be on a diet in accordance with the American Academy of Pediatrics guidelines (1) or equivalent.
- If the prefilled syringe becomes available: Data collection on alirocumab administration and alirocumab compliance check by review of diary and treatment kit accountability.
- Check of stability of background LMT.
- IVRS/IWRS contact to get treatment kit number for 1 kit resupply.

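### In the extension, the visit text allocates one kit per 12-weekly supply to every patient, which contradicts Section 8.5 for Cohorts 1 and 2 and the 300 mg Q4W group

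*Protocol*

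**What the plan says.** **Visit text.** At the first extension visit, Protocol 10.1.4.1 asks for "IVRS/IWRS contact for open-label extension treatment allocation of one 7-digit treatment kit number". At the later visits, which alternate so that one falls every 12 weeks, 10.1.4.4 and 10.1.4.5 both say "IVRS/IWRS contact to get treatment kit number for 1 kit resupply". None of the three separates cohorts or doses, although 10.1.4.4 and 10.1.4.5 do separate the cohorts for lipid sampling.

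**Supply text.** For the extension with prefilled syringes, Protocol 8.5 says of the two Q2W cohorts: "Cohorts 1 & 2: patients will receive 2 kits for 12-weeks alirocumab treatment period. Each kit will contain 4 PFS". The third cohort is allotted a single four-syringe kit over the same span. For the last cohort the count varies: "Cohort 4: patients will receive 1 or 2 kit(s) of PFS for up to a 12 week alirocumab treatment period, depending on dose group".

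The split by dose and the kit size for Cohort 4 are spelled out for the main phase: "1 kit for 150mg Q4W & 2 kits for 300mg Q4W). Each kit will contain 4 PFS of alirocumab 150 mg/mL".

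**Dosing text.** Protocol 10.1.4.1 sets the extension intervals: "The alirocumab injections should be done every 2 weeks for Cohorts 1 and 2 or every 4 weeks for Cohort 3 and Cohort 4". Section 8.1 gives one syringe per Q2W dose and two per 300 mg dose. Section 8.4 puts syringe allocation at every 3 months.

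**The concern.** The number of kits handed over at a 12-weekly visit fixes how many doses a patient can take before the next one. Two operative parts of the same protocol give different numbers for Cohorts 1 and 2 and for the 300 mg group. The text for Visits 9 and 10, which fall between the first two supplies, names no kit, so no scheduled top-up closes the difference.

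What is at stake is the reading of the extension data. SAP 2.4.4.2.4 defines the combined efficacy period as running from the first injection to the last extension injection plus 21 days (Cohorts 1 and 2) or 35 days (Cohorts 3 and 4). A dosing gap in mid-extension does not interrupt that period. An LDL-C drawn at the end of such a gap would therefore enter the on-treatment summaries. During the extension the lipid values also go to the investigator (Protocol 8.3.2), who would see a value taken off drug without the plan having intended it.

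**Working it through.** **Inputs**
- Interval between supplies: 12 weeks (Protocol 8.4, 8.5 and the extension flow charts).
- Syringes per kit: 4 (8.5). For Cohort 4 this is stated for the main phase and assumed for the extension.
- Dosing interval: 2 weeks for Cohorts 1 and 2, 4 weeks for Cohorts 3 and 4 (10.1.4.1).
- Syringes per dose: 1, except 2 for 300 mg (8.1).

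**Step 1: reproduce Section 8.5.** Syringes needed = (12 / dosing interval) × syringes per dose. Kits needed = that number / 4, rounded up.

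| Regimen | Doses in 12 weeks | Syringes needed | Kits needed | Section 8.5 | Visit text |
|---|---|---|---|---|---|
| Q2W, Cohorts 1 and 2 | 12/2 = 6 | 6 × 1 = 6 | 6/4 → 2 | 2 | 1 |
| Cohort 3, Q4W | 12/4 = 3 | 3 × 1 = 3 | 3/4 → 1 | 1 | 1 |
| Cohort 4, 150 mg Q4W | 3 | 3 × 1 = 3 | 3/4 → 1 | 1 or 2 by dose (main phase: 1) | 1 |
| Cohort 4, 300 mg Q4W | 3 | 3 × 2 = 6 | 6/4 → 2 | 1 or 2 by dose (main phase: 2) | 1 |

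The 8.5 counts cover every original regimen. The visit text covers two of the four rows.

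**Step 2: doses not covered by one kit.**
- Q2W: 4 syringes supply 4 of 6 injections; 2/6 = 33% uncovered.
- 300 mg Q4W: 4 syringes supply 2 of 3 doses; 1/3 = 33% uncovered.

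Over the whole schedule in the flow charts, with no top-up:
- Q2W, Weeks 16 to 128: (128 − 16)/2 + 1 = 57 doses. Nine full intervals at 2 missed each give 18/57 = 31.6%; the last interval is short and is covered.
- 300 mg Q4W, Weeks 12 to 44: 9 doses, 3 missed, 33.3%.

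These schedules are upper bounds, since the protocol ends dosing by December 2018.

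**Step 3: timing of the next LDL-C.** Assume syringes are used on schedule from the supply visit.
- Q2W: doses at weeks 0, 2, 4 and 6. The week-12 sample falls (12 − 6) × 7 = 42 days after the last dose, against a 21-day on-treatment limit. With full supply it would be (12 − 10) × 7 = 14 days.
- 300 mg Q4W: doses at weeks 0 and 4. The sample falls (12 − 4) × 7 = 56 days after the last dose, against 35. With full supply it would be (12 − 8) × 7 = 28 days.

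**Step 4: Cohort 3 after the switch.** Protocol 8.1 moves Cohorts 1 to 3 to the selected Phase 3 doses. The SAP appears to treat those as Q2W: 2.1.4 gives switched Cohort 3 patients 21 rather than 35 days, and 2.4.3.1 adds 14 days to post-switch exposure. A Q2W regimen needs 6 syringes per 12 weeks, while 8.5 still lists Cohort 3 at 1 kit (4 syringes). In that case 8.5 itself would fall short for these patients.

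**The case against.** The strongest reply is that the site does not choose the kit count. Kit numbers come from the IRT, and other text leaves room for several kits: 8.1.2 for Cohorts 1 and 2, 8.7.1, footnote g of the Cohorts 1 to 3 extension flow chart, and the bullet on prefilled syringes that follows the singular wording in 10.1.4.1. Section 8.4 permits allocation at unscheduled visits for Cohorts 1 to 3, and the flow chart allows more frequent visits depending on supplies. In Cohort 4, flow chart footnote d has site staff giving the injections, so a shortage would be noticed. Accountability checks and mean injection frequency (SAP 2.4.3.2) would also leave a trace.

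Most of this stands, and it limits the consequence. A reader might infer that a third of doses will go without drug, that all patients are affected, or that long-term efficacy will be understated. The documents support none of these. The IRT table is not in them, one kit is enough for Cohort 3 on its original doses and for 150 mg Q4W, and no size of bias can be derived. Vial supply lies outside the sum altogether: a vial kit holds one vial and allocation is every 2 or 4 weeks.

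The reply does not remove the contradiction. The mixed singular and plural wording shows that the passages disagree. The allowance for unscheduled allocation in 8.4 is not repeated for Cohort 4, and 8.1.2 uses the singular for Cohorts 3 and 4. For the combined period the SAP reports mean injection frequency only, without the under-dosing measure used in the main phase.

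**Conclusion.** The contradiction is certain. Sections 10.1.4.1, 10.1.4.4 and 10.1.4.5 refer to one kit per supply without a split, and 8.5 does not. At four syringes per kit, one kit falls a third short of 12 weeks for Q2W and for 300 mg Q4W.

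The loss of doses is conditional. It needs prefilled syringes in use, a site or the IRT following the visit text rather than 8.5, and no unscheduled resupply. For the 300 mg group it also rests on the main-phase kit size carrying over to the extension. If all of that held, up to a third of extension doses in those groups could go unsupplied, and LDL-C values taken 42 or 56 days after the last available dose would be summarised as on-treatment.

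Only the descriptive extension results are exposed. The Week 8 endpoints, the Cohort 4 Week 12 endpoint and the dose-selection analyses use main-phase data. This should be fixed, but it does not threaten the trial's main conclusions.

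**What to change.** Reconcile 10.1.4.1, 10.1.4.4 and 10.1.4.5 with 8.5. The simplest way is to replace the fixed count in the visit sections with a reference to the 8.5 kit counts, and to state those counts by the regimen the patient is on at that visit rather than by original cohort. That wording should cover Cohort 3 patients who switch to a Q2W Phase 3 dose. It should also confirm the kit size for Cohort 4 in the extension.

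The rule should be that the syringes supplied at least cover the scheduled injections. Exact equality is not achievable with four-syringe kits: 6 needed means 8 supplied, and 3 needed means 4 supplied. Then check that the IRT dispensing table agrees.

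The cost is wording in three visit sections and 8.5, plus one system check. No visits, samples or patients are added, and no dose or clinical rule is changed.
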